#### **1.3.3 Screening period/Baseline**

Screening evaluations must be performed no more than 28 days prior to registration. The subject must begin study treatment no more than 14 days after registration. Baseline research blood and tumor samples may be performed anytime prior to the start of therapy. Ideally, the research blood samples should be collected 3-14 days prior to the tumor biopsy, but it is also acceptable to collect them on the same day.

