#### **1.7.11 TOXICITY MONITORING AND ADVERSE EVENT REPORTING**

All patients who receive one dose of protocol therapy will be evaluable for assessment of toxicity. Prior to each cycle the treating physician will fully assess the patient's condition with respect to possible treatment related toxicities. All adverse events, whether observed by the physician or reported by the patient, occurring during the active portion of therapy, or up to 30 days after the last dose of treatment will be graded by a numerical score according to the NCI's Common Terminology Criteria for Adverse Events (CTCAE), Version 4.0

(<http://ctep.cancer.gov/reporting/ctc.html>) and recorded in the patient's medical record. For the purposes of reporting laboratory abnormalities, only Grade 3-4 adverse events will be recorded on the adverse event CRF pages. Grade 1-2 laboratory abnormalities will not be recorded on the adverse event CRF pages, unless the investigator judges it to be clinically significant and wishes to report it. Information entered on the adverse event CRF pages will include:

- Specific type and duration of reaction (i.e., start and stop dates, resolution).
- Severity/grade.
- Relationship to study drug (causality, attribution).
- Management of the event, if treated with medication and other actions taken to alleviate the clinical event.
- Whether or not it was considered a SAE.

A preexisting condition is one that is present at the start of the study. A preexisting condition will be recorded as an adverse event if the frequency, intensity, or the character of the condition worsens during the study period.

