### **Adverse Event Reporting Requirements**

An adverse experience is defined as any unintended or abnormal clinical observation that is not of benefit to the patient. Either the condition was not present prior to exposure to the study therapy, or it has worsened in intensity or frequency following exposure to the study therapy.

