### **SAE Reporting Period**

The SAE reporting period starts at start of treatment and lasts through 30 days after the patient's last dose or start of subsequent therapy, whichever comes sooner. SAE's that during screening period prior to the start of therapy are presumed to be unrelated to the study and need not be reported as SAEs.

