### **Definition of Related**

There is a reasonable possibility that the drug caused the adverse experience. That is, the event is judged by the investigator to be possibly, probably or definitely related to the treatment.

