### **Tumor Biopsy and Venipuncture Risks**

There is a small risk of bleeding, pain, or infection with tumor biopsies. These risks will be minimized by use of adequate hemostasis, local anesthetic and aseptic technique. This level of risk is considered to be acceptable as patients routinely have similar biopsies performed when pathologic evaluation is necessary to confirm diagnosis or a site of tumor progression. Tumor biopsies are mandatory, however, may be omitted without deviation due to unacceptable risk (warfarin therapy, tumor near location with high risk for bleeding or other complication, etc.) with prior authorization from the PI (see PI contact information on cover page of protocol). There is a very small risk of bleeding, pain, or infection with venipuncture; however this is minimized as the correlative blood samples are being taken at the same time as the standard of care laboratory bloods.

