### **Frequency Of Data Collection**

Data is collected at each study visit and follow-up contact. Safety data collection (including SAEs) starts after the first study treatment.

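### Serious complications of the pre-dose research biopsy are presumed unrelated to the study and need not be reported

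*Combined protocol and SAP*

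**What the plan says.** Section 1.7.11, SAE Reporting Period, sets the window: "The SAE reporting period starts at start of treatment and lasts through 30 days after the patient's last dose", or until subsequent therapy begins if that is sooner. It adds that SAEs in screening "prior to the start of therapy are presumed to be unrelated to the study and need not be reported as SAEs". Section 6.3, Frequency Of Data Collection, agrees: "Safety data collection (including SAEs) starts after the first study treatment".

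The wider AE rules in section 1.7.11 have the same starting point. Events "occurring during the active portion of therapy, or up to 30 days after the last dose of treatment will be graded" and recorded. An adverse experience is defined by reference to drug exposure: "Either the condition was not present prior to exposure to the study therapy, or it has worsened in intensity or frequency" after that exposure. Relatedness is also defined through the drug: "There is a reasonable possibility that the drug caused the adverse experience".

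On the biopsy, section 1.3.3 says: "Baseline research blood and tumor samples may be performed anytime prior to the start of therapy". Section 1.8, footnote 6 of both treatment calendars and Appendix B list research biopsies at baseline, Week 1 and Week 7. Section 4.1.8 says: "There is a small risk of bleeding, pain, or infection with tumor biopsies".

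**The concern.** A presumption that pre-dose SAEs have nothing to do with the study is reasonable when nothing has been done to the patient for the study's sake. That is not so here. Consent precedes any research procedure (section 4.1.5), and the baseline biopsy serves only the correlative analyses. A patient admitted with bleeding or infection after it, before the first capsule, meets the protocol's own SAE definition because of something the study did. The text presumes otherwise and asks for no report.

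What is at stake is subject protection and what the oversight bodies can see. The IRB, the Office of Human Research Services (OHRS) and the Human Research Oversight Committee (HROC) could remain unaware of such an event while the study goes on urging patients to have biopsies.

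**Working it through.** The documents state no figure to reproduce, so the check is to put the rules in time order.

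1. **Consent to first dose.** Screening evaluations may be done up to 28 days before registration, and treatment must begin within 14 days after it (section 1.3.3). If the biopsy is taken inside the screening window, the interval from biopsy to first dose runs from the same day up to 28 + 14 = 42 days. The documents set no separate limit on how early the biopsy may be.

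2. **An SAE in that interval.** Four texts bear on it: the SAE window, the AE recording window, the AE definition, and the start of safety data collection in section 6.3. All four are tied to treatment or exposure, and none makes an exception for study procedures. The screening sentence then adds the presumption of unrelatedness. No text seen requires an SAE report.

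3. **If the event prevents dosing.** Under Missing data in section 6.1, subjects who never start treatment are replaced, up to 5 times. Both definitions of evaluable for toxicity (sections 1.7.11 and 6.1) require dosing. Such a subject therefore leaves the toxicity population with no SAE record required.

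4. **A complication that appears after the first dose.** It is inside the window even if the biopsy came earlier, because the window applies to events and not to biopsies.

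5. **Week 1 and Week 7 biopsies.** These follow the start of the lead-in, so their complications are recorded as AEs, with a field for seriousness. The causality field, however, asks about study drug, and relatedness is defined by the drug. SAE Reporting Timeline opens with drug-related events only, then requires other SAEs to go to the IRB within 3 to 10 days. Whether that second rule covers a procedure-related SAE is unclear.

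6. **Size.** One baseline biopsy per subject × 12-27 planned subjects = 12-27 biopsies at most. If replacements are counted on top of the planned sample, the upper end is 27 + 5 = 32. The number actually done depends on a conflict in the text: section 1.8, the calendars and Appendix B make research biopsies optional, while section 4.1.8 calls them mandatory unless the PI authorizes omission for risk. With no complication rate stated, no number of missed events can be derived.

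7. **Primary endpoint.** DLTs are counted from Day -14, the first day of treatment, so a pre-dose biopsy event cannot enter the MTD decision under either rule.

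**The case against.** The best case for the plan has four parts.

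- **The rule does not forbid reporting.** It says only that reporting is not needed. Both calendars ask about baseline symptoms and adverse events at Screening and Week -2, so a complication could be noted. This stands, and it rules out saying that such events are never captured. But the calendar check carries no SAE duty, and the event could be entered as a preexisting condition.
- **Later biopsies are covered.** A reader might infer from the drug-only definition of relatedness that no biopsy SAE is reportable at any visit, that oversight would see none whatever the true rate, and that all 36-81 possible biopsies (3 × 12 to 3 × 27) escape. The documents do not support this. All AEs in the treatment window are recorded whatever their cause, HROC monitors SAEs without restriction to drug-related ones (section 6.3), and the reporting text can be read to cover other SAEs. What remains for Weeks 1 and 7 is an ambiguity and a missing attribution option.
- **Some baseline complications fall inside the window.** The biopsy may be done close to the first dose, and later-appearing effects are then collected. This also stands. The gap is limited to events that arise before dosing.
- **The institutional monitoring plan may say more.** Section 6.3 defers to it and it is not among the documents. It might impose a reporting duty, but the protocol text would then contradict it.

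None of this supplies a rule that requires a pre-dose biopsy SAE to be reported.

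**Conclusion.** The concern holds for the interval between the baseline research biopsy and the first dose. There the protocol presumes a study-caused SAE to be unrelated and does not require it to be reported. The exposure is at most one biopsy per subject, up to 12-27 for the planned sample, and lower to the extent that biopsies are optional. For Weeks 1 and 7 the finding is weaker: events are recorded, but a procedure cause has no place in the attribution field and the reporting duty is ambiguous.

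This is a defect in safety oversight. It does not bias the MTD or DLT assessment. The conclusion assumes that no document outside the protocol imposes a reporting duty from consent. It makes no claim about how often complications occur. The change should be made because it protects subjects and costs little.

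**What to change.** - **SAE Reporting Period (1.7.11) and Frequency Of Data Collection (6.3):** collect and report AEs and SAEs related to a research procedure (tumor biopsy or research blood draw) from signed consent, and remove the presumption of unrelatedness for them. Keep the start of treatment as the start for all other events.
- **AE recording window, AE definition and causality field (1.7.11):** align these with that change. If they stay tied to drug exposure, a new inconsistency results.
- **Definition of Related:** extend it to study drug or study procedure.
- **SAE Reporting Timeline:** state that procedure-related SAEs go to OHRS and the IRB, which also settles the Week 1 and Week 7 ambiguity.
- **Biopsy status:** reconcile section 4.1.8 with section 1.8, the calendars and Appendix B.

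The cost is amendment wording in these places, one more attribution option on the AE eCRF, and a few additional pre-dose AE records. No visit or procedure is added.

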### **SAE Reporting Timeline**

All "unexpected" (defined below) and/or "serious" (defined below) adverse events related to pembrolizumab/nivolumab or the combination of pembrolizumab/nivolumab + trigriluzole and occurring during the active portion of therapy, or up to 30 days after the last dose of treatment, will be reported to the Office of Human Research Services at [contact] or [contact]. Events will be promptly reported, in writing, to the local IRB in accordance with IRB policy. If a death occurs the IRB will be notified **within 24-hours** of initial receipt of information. All other SAEs must be reported to the IRB **within 3 to 10 days** of initial receipt of information. Written follow-up reports are required when additional information is needed to fully characterize the event. Copies of each report sent to the IRB will be kept in the study regulatory file.

Collaborating institutions will report all SAEs to RCINJ Office of Human Research Services (OHRs) and RCINJ OHRs will be responsible for forwarding SAE reports to the IRB, FDA, Fox Chase Chemical Diversity Center, Inc. and Biohaven Pharmaceuticals.

In addition to reporting to the local IRB, reporting to external bodies such as industry and/or the FDA may be necessary.

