### **1.3.4 Active phase, lead-in period**

During the 14-day lead-in period, subjects will take trigriluzole monotherapy. The 14-day period is: Week -2 and Week -1.

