### **1.7.7 Dose Modifications and Withholding**

As toxicity of these agents is largely non-overlapping, management of toxicity is dependent on which agent is more likely to have resulted in the toxicity. Vertigo, somnolence, and circumoral paresthesia should be attributed to trigriluzole. Immune-related adverse events should be attributed to the anti- PD-1 antibody. Refer to agent-specific management instructions below for dose modifications and holdings.

*Overlapping toxicities of trigriluzole and anti- PD-1 antibody include fatigue, asthenia, nausea, dizziness, diarrhea, anorexia and liver injury. When these toxicities occur, both drugs should be held until toxicity resolves to grade 0-1.*

Study therapy (both agents) may be held for up to 6 consecutive weeks. Subjects who are not able to resume at least 1 study drug within a period of 6 weeks should be removed from the active treatment phase of the study and begin follow-up procedures.

Dosing interruptions are permitted in the case of medical / surgical events or logistical reasons not related to study therapy (e.g., elective surgery, unrelated medical events, patient vacation, and/or holidays). Missed doses should be omitted, not delayed. Subjects should be placed back on study therapy within 3 weeks of the scheduled interruption, unless otherwise discussed with the study PI or co-PI. The reason for interruption should be documented in the patient's study record. Tumor assessments should continue per the study calendar even if study medication was missed.

Delays due to holidays, weekends and bad weather will be permitted and will not be counted as a protocol violation, and efforts will be made to get the patient back on the original schedule so that assessments are uniform across subjects. If correlative samples are collected and the scheduled treatment that day is delayed/held for any reason, there is no need to re-collect correlative samples.

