### **Reporting SAEs for Investigational Agent Trigriluzole**

The PI shall notify the FDA of any adverse experience related to the use of trigriluzole or the combination of pembrolizumab/nivolumab + trigriluzole that is both serious and unexpected, as soon as possible and in no event later than 15 calendar days after the PI's discovery of the event. Each written notification may be submitted on FDA Form MedWatch 3500A <http://www.fda.gov/medwatch/safety/3500a.pdf> (fax # [name]).

The PI shall also notify the FDA by telephone or by facsimile transmission of any unexpected fatal or life-threatening experiences associated with the use of trigriluzole or the combination of pembrolizumab/nivolumab + trigriluzole, as soon as possible but no later than 7 calendar days from the PI's discovery of the event information.

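### The rule for prompt reporting to OHRS leaves out events related to trigriluzole alone and disagrees with the protocol's other safety-reporting text

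*Combined protocol and SAP*

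**What the plan says.** Section 1.7.11 sets several reporting rules with different scopes.

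- **SAE Reporting Timeline, opening sentence.** Unexpected and/or serious "adverse events related to pembrolizumab/nivolumab or the combination of pembrolizumab/nivolumab + trigriluzole" go to OHRS if "occurring during the active portion of therapy, or up to 30 days after the last dose of treatment". Prompt written reporting to the local IRB follows, under IRB policy.
- **Same section, later sentences.** "If a death occurs the IRB will be notified" within 24 hours. "All other SAEs must be reported to the IRB" within 3 to 10 days. Neither sentence mentions attribution. Collaborating institutions send all SAEs to OHRS, which forwards SAE reports to the IRB, the FDA and the two supporting companies.
- **SAE Reporting Period.** The period begins with the start of treatment.
- **Reporting SAEs for Investigational Agent Trigriluzole.** The FDA is told of an experience "related to the use of trigriluzole or the combination of pembrolizumab/nivolumab + trigriluzole that is both serious and unexpected", within 15 calendar days. Unexpected fatal or life-threatening events are due within 7.

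Two other sections bear on attribution. Section 1.3.4 says: "During the 14-day lead-in period, subjects will take trigriluzole monotherapy". Section 1.7.7 says: "Vertigo, somnolence, and circumoral paresthesia should be attributed to trigriluzole".

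**The concern.** Trigriluzole is the one agent the protocol labels investigational (section 1.7.4) and the one whose dose is escalated (Table 3). The antibodies are commercial products. Yet the sentence that starts prompt reporting to OHRS names the antibodies and the combination, and not trigriluzole by itself.

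The missing category will arise. In the lead-in no on-study antibody has been given, so an event caused by a study drug can only be ascribed to trigriluzole. During combination treatment, section 1.7.7 tells investigators to ascribe certain events to trigriluzole, which takes them outside the opening sentence.

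At stake is whether staff at the lead site know that such an event needs an expedited notice. OHRS is also the office charged with forwarding SAE reports, so notice to OHRS starts that chain.

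**Working it through.** The plan gives no figure here and no arithmetic applies. The check is to take an event judged related to trigriluzole alone, occurring at the lead site, and ask which reporting rule reaches it.

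| Rule (section 1.7.11) | Recipient | Serious and unexpected | Serious but expected | Unexpected, not serious |
|---|---|---|---|---|
| Opening sentence, SAE Reporting Timeline | OHRS, then IRB | Not listed | Not listed | Not listed |
| Sentence on deaths | IRB | Yes, if fatal | Yes, if fatal | Does not apply |
| Sentence on all other SAEs | IRB | Yes if read alone; no if it inherits the opening scope | Same | No |
| Sentence on collaborating institutions | OHRS, then onward | Not addressed to the lead site | Same | No |
| Rule for commercial drugs | FDA | No, antibody only | No | No |
| Rule for trigriluzole | FDA | Yes | No | No |

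Four things follow.

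1. **OHRS.** No row gives the lead site a duty to notify OHRS promptly of a trigriluzole-only event. The collaborating-institutions row does not fill the gap: section 2.3 lists one research site and section 3.0 marks multi-site coordination as not applicable.
2. **IRB.** For serious events the answer depends on whether the sentence on all other SAEs stands alone or takes its scope from the opening sentence. The text does not say.
3. **Unexpected, non-serious events.** The opening sentence sends this class to OHRS when the cause is the antibody or the combination. For trigriluzole alone the column contains no route at all.
4. **Which text is out of line.** The FDA rule names trigriluzole alone. The DLT definition (section 6.1) counts events related to either drug or to the two together. The SAE reporting period includes the lead-in, because treatment starts on Day -14 (section 1.3). Only the opening sentence has the narrower scope, which points to a drafting omission.

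**The case against.** The best defence is that little escapes in practice, and much of it stands.

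- Read alone, the sentences on deaths and on all other SAEs give serious trigriluzole-only events an IRB route.
- Section 1.7.11 requires adverse events to be graded and recorded whatever the cause, with causality and SAE status on the form; only Grade 1-2 laboratory abnormalities are routinely left off. OHRS coordinators complete the electronic forms (section 6.2), with treatment forms due within 14 days of each cycle. OHRS therefore does receive the data. What it lacks is an expedited notice.
- The three symptoms assigned to trigriluzole in section 1.7.7 appear in section 1.4.2 among the common riluzole events. Unless serious, they would rarely trigger expedited reporting under any attribution.
- IRB reporting follows an IRB policy that is not in the documents and may be broader.

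A reader might go further and infer that serious trigriluzole events simply fall outside OHRS and IRB reporting. The unqualified IRB sentences do not support that.

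A reader might also infer that dose escalation would proceed blind to trigriluzole toxicity. It would not. DLTs cover either drug, the DLT observation period starts on Day -14, the study team reviews all toxicity for weekly Phase I meetings, and the oversight committee (HROC) reviews all DLTs (sections 6.1 and 6.3).

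Nor should the gap be sized by the lead-in's share of the five-week DLT observation period (14/35 = 40%). That is exposure time, not missed reports, and DLT capture does not use this sentence. Even in the lead-in, an event could be ascribed to an earlier antibody: prior PD-1 or PD-L1 therapy is allowed (inclusion criterion 6), and section 1.7.7 notes reactions months after the last dose.

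None of this supplies the missing OHRS notice or settles the scope of the IRB sentence.

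**Conclusion.** The point holds as an internal inconsistency in the safety-reporting text, and it should be corrected. Followed literally at the lead site, the SAE reporting sections give no expedited OHRS notice of serious trigriluzole-only events and leave their IRB route ambiguous, apart from deaths. They give no route for unexpected but non-serious trigriluzole-only events.

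The reach is limited. Sample size, escalation rule, DLT counting and data capture are unchanged, and the documents give no basis for estimating how many reports would be affected. The conclusion assumes that the opening sentence is applied as written and that no institutional policy outside the documents widens it.

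**What to change.** Amend the opening sentence of SAE Reporting Timeline so that its scope reads: *related to trigriluzole, to pembrolizumab/nivolumab, or to the combination*. It then agrees with the SAE reporting period, the FDA rule for trigriluzole and the DLT definition. It also removes the conflict with the section's own unqualified IRB sentences as far as trigriluzole-only events are concerned.

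The cost is one phrase in an amendment and a few more reports. No dose, visit, sample size or analysis changes.
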